2.5.2.3 Dose intensity and relative dose intensity

Dose intensity (DI) for patients with non-zero duration of exposure is defined as follows:

$DI \text{ (dosing unit / unit of time)} = \text{Actual Cumulative dose (dosing unit)} / \text{Duration of exposure (unit of time)}$.

For example, for INC280, the dosing unit is mg and actual cumulative dose is 1200 mg, and the unit of time is a day and duration of exposure is 18 days, then

$$\begin{aligned} DI \text{ (mg/day)} &= \text{Actual Cumulative dose (mg)} / \text{Duration of exposure (day)} \\ &= 1200 \text{ (mg)} / 18 \text{ (day)} = 66.7 \text{ (mg/day)} \end{aligned}$$

For patients who did not take any drug the DI is by definition equal to zero.

Planned dose intensity (PDI) is defined as follows:

$PDI \text{ (mg / day)} = \text{Planned Cumulative dose (mg)} / \text{Duration of exposure (day)}$.

Relative dose intensity (RDI) is defined as follows:

RDI = DI (mg / day) / PDI (mg / day).

DI and RDI will be summarized for the study drug. The RDI will be tabulated using the following intervals: <0.5, >=0.5-<0.75,>=0.75-<0.9, >=0.9-<1.1, >=1.1.

2.5.2.4 Dose reductions, interruptions or permanent discontinuations

The number of patients who have dose reductions, permanent discontinuations or interruptions, and the reasons, will be summarized for the study drug.

‘Dose interrupted’, and ‘Dose permanently discontinued’ fields from the Dosage Administration CRF pages (DAR) will be used to determine the dose interruptions, and permanent discontinuations, respectively. Dose reductions will be derived programmatically using the dosing information as described below.

The corresponding fields ‘Reason for dose change/dose interrupted’ and ‘Reason for permanent discontinuation’ will be used to summarize the reasons.

A dose change is either ‘change in prescribed dose level’ or ‘dosing error’ where actual dose administered/total daily dose is different from the prescribed dose.

For the purpose of summarizing interruptions and reasons, in case multiple entries for interruption that are entered on consecutive days with different reasons will be counted as separate interruptions. However, if the reason is the same in this mentioned multiple entries on consecutive days, then it will be counted as one interruption.

Dose reduction: A dose change where the prescribed dose level is lower than the previous prescribed dose level or where the actual dose administered/total daily dose is lower than the calculated dose amount based on the prescribed dose. Therefore any dose change to correct a dosing error will not be considered a dose reduction. Only dose change is collected in the CRF, number of reductions will be derived programmatically based on the change and the direction of the change.

2.6 Analysis of the qualifying adverse events within first four weeks of treatment for dose determination

A two-parameter Bayesian Logistic Regression Model (BLRM) guided by the Escalation with Overdose Control (EWOC) principle will be used for the safety analysis. This safety analysis (to be performed during the dose decision analysis after the Dose-Determining Part as well as to confirm the Expansion Part dose) will be based on data (occurrence/absence) of certain AEs within the first 28 days treatment. Doses available for consideration as the Expansion Part dose will be those estimated under the modeling for which the risk that the true rate of the qualifying AE in the first four weeks of treatment exceeds 33% is less than 25%.

The DDS will be used for these analyses.

The Bayesian approach requires the specification of prior distributions for the model parameters. All information currently available about the dose-AE relationships of single agent INC280 will be summarized in prior distributions. More details can be found in [CINC280X2201-Protocol-Appendix 5](#).

Dose recommendation will be based on posterior summaries including the mean, median, standard deviation, 95%-credibility interval, and the probability that the true rate of qualifying AEs lies in one of the following categories:

- [0,16%] under-dosing
- [16%,33%] targeted toxicity
- [33%,100%] excessive toxicity

Following the principle of EWOC, at the end of Dose-Determining Part, a range of doses will be recommended for the Dose Expansion Part. The highest dose level in that dose range will be the highest dose that satisfies the overdose criterion that there is less than 25% chance of excessive toxicity. If the recommended Dose Expansion Part dose as per the PK analysis (See [CINC280X2201-Protocol sections 10.5.4.1.1 and 6.2.2](#)) is higher than the dose allowed by the BLRM, the highest dose allowed by the BLRM will be used for the Dose Expansion Part.

Summaries of the posterior distribution of rate of qualifying AEs based on the AE data from all patients in the DDS will be presented.

2.7 Analysis of the primary objective

2.7.1 Primary endpoint

The primary variable for analysis is Time to progression (TTP), as per local assessment, is defined as the time from the date of baseline evaluation to the date of the first documented radiological confirmation of disease progression or death due to underlying cancer (RECIST v1.1). If a patient has not had the event at the date of analysis cut-off or when he/she received any further anti-neoplastic therapy, TTP will be censored at the time of the last adequate assessment.

2.7.2 Statistical hypothesis, model, and method of analysis

The primary TTP analysis will include all patients in the FAS (on an Intention-to Treat (ITT) basis) with patients classified according to the treatment group they were assigned to, at baseline (Dose-Determining Part or Expansion Part dose).

For patients in the Dose-Determining Part, TTP will be listed along with overall response.

For patients treated at the Expansion Part dose, the distribution of TTP will be estimated using the Kaplan-Meier method. The number of censored patients and number of patients with the event along with the median TTP and quantiles (along with one-sided 90% confidence intervals) at 3 months, 6 months, 9 months and 1 year will be presented. Also, the reason of censoring will be summarized and listed for each patient.

2.7.3 Handling of missing values/censoring/discontinuations

If a patient has not experienced a radiological disease progression or death due to underlying cancer, TTP will be censored at the date of the last adequate tumor assessment, defined as the date the last tumor assessment with overall lesion response of CR, PR or SD which was made

before a censoring reason occurred, or the date of first dose of INC280 if no post-baseline assessments are available (See RECIST v1.1).

Other missing data will simply be noted as missing on appropriate tables/listings. The FAS will be used.

2.8 Analysis of the efficacy variables

Evaluation of anti-tumor activity will be based on local radiologic examinations of overall lesion response according to RECIST v1.1 (refer [CINC280X2201-Protocol-Appendix 1](#)). The variables used to evaluate anti-tumor activity are ORR, DCR, BOR, PFS as per RECIST v1.1 and OS. Summaries and listings described in this section will be done based on the FAS.

Individual lesion measurements, overall lesion response will be listed by patient. ORR, DCR and BOR will be summarized ([Table 2-2](#)) by study treatment group and by cMET status. Whereas PFS and OS will be summarized using Full analysis set.

Individual lesion measurements and overall response (investigator's assessment) at each assessment will be listed by patient and treatment group. BOR will be summarized for all patients by treatment group and the observed ORR will be summarized in terms of percentage rates with 95% confidence intervals for each treatment group. The Kaplan-Meier estimates of OS and PFS distribution functions will be presented graphically. The resulting median OS and median PFS and quantile estimates will be provided along with 95% confidence intervals. Rate estimates of PFS and OS (along with 95% CI) at 3 months, 6 months, 9 months and 1 year will be presented, as given by the Kaplan-Meier analysis.

For treatments groups with less than 10 patients, Kaplan-Meier estimates and plots will not be presented.

Table 2-2 Analysis of the efficacy variables

Endpoint	Definition	Analysis
PFS	PFS is defined as the time from date of first study treatment intake to the date of the first radiologically documented progression or death due to any cause or initiation of new antineoplastic therapy.	The number of censored patients and number of patients with the event along with the resulting median PFS and quantile estimates will be provided along with 95% confidence intervals using Kaplan Meier method.
OS	OS is defined as the time from date of first study treatment intake to date of death due to any cause	The number of censored patients and number of patients with the event along with the resulting median OS and quantile estimates will be provided along with 95% confidence intervals using Kaplan Meier method.

BOR	The best overall response (BOR) is the best response recorded from the start of the treatment until disease progression/recurrence.	BOR will be summarized as observed proportion in each category, and corresponding 95% confidence intervals (CIs) based on the exact binomial distribution will be presented. Tumor volume best change from baseline will be presented graphically (waterfall graphs).
ORR	Proportion of patients with a best overall response of confirmed CR or PR at any time on study per RECIST.	ORR and corresponding 95% confidence intervals (CIs) based on the exact binomial distribution will be presented.
DCR	Proportion of patients with a BOR of CR, PR or SD at any time on study per RECIST.	DCR and corresponding 95% confidence intervals (CIs) based on the exact binomial distribution will be presented.

2.9 Safety analysis

Summaries and listings described in this section will be done by study treatment groups based on the Safety set.

2.9.1 Adverse events

2.9.1.1 Coding of AEs

Adverse events are coded using the Medical dictionary for regulatory activities (MedDRA) terminology. The latest available MedDRA version at the time of the analyses should be used. The MedDRA version used should be specified in the footnote of relevant tables.

2.9.1.2 Grading of AEs

AEs will be assessed according to the Common Terminology Criteria for Adverse Events (CTCAE) version 4.03.

The CTCAE represents a comprehensive grading system for reporting the acute and late effects of cancer treatments. CTCAE grading is by definition a 5-point scale generally corresponding to mild, moderate, severe, life threatening, and death. This grading system inherently places a value on the importance of an event, although there is not necessarily proportionality among grades (a grade 2 is not necessarily twice as bad as a grade 1).

2.9.1.3 AE summaries

AE summaries will include all AEs occurring during on-treatment period (Section 2.1.1). All AEs collected in the AE (e)CRF page will be listed along with the information collected on those AEs e.g. AE relationship to study drug, AE outcome etc. AEs starting during the post-treatment period will be flagged in the listings.

AEs will be summarized by number and percentage of patients having at least one AE, having at least one AE in each primary system organ class (SOC) and for each preferred term (PT) using MedDRA coding. A patient with multiple occurrences of an AE will be counted only

once in the respective AE category. A patient with multiple CTCAE grades for the same preferred term will be summarized under the maximum CTCAE grade recorded for the event. AE with missing CTCAE grade will be included in the 'All grades' column of the summary tables.

In AE summaries the SOC will be presented alphabetically and the PTs will be sorted within primary SOC in descending frequency, based on their frequency in the 'All Patients' column.

The following AE summaries will be produced by study treatment group:

- Overview of AE
- AEs regardless of study treatment relationship by SOC, PT and maximum grade
- AEs regardless of study treatment relationship by PT and maximum grade
- AEs suspected to be study treatment related by PT and maximum grade
- SAEs regardless of relationship to study treatment by PT and maximum grade
- SAEs suspected to be study treatment related by PT and maximum grade
- Summary of qualifying AE for dose decision analysis (Dose determining part only)
- AEs leading to discontinuation of study treatment regardless of relationship to study treatment by PT and maximum grade
- AEs leading to discontinuation of study treatment suspected to be study treatment related by PT and maximum grade
- AEs requiring dose adjustment/interruption by SOC, PT and maximum grade
- AEs requiring additional therapy by SOC, PT and maximum grade

Additionally, for the legal requirements of ClinicalTrials.gov and EudraCT, two required tables on on-treatment adverse events which are not serious adverse events with an incidence greater than 5% and on on-treatment serious adverse events and SAE suspected to be related to study treatment will be provided by system organ class and preferred term on the safety set population.

If for a same patient, several consecutive AEs (irrespective of study treatment causality, seriousness and severity) occurred with the same SOC and PT:

- a single occurrence will be counted if there is ≤ 1 day gap between the end date of the preceding AE and the start date of the consecutive AE
- more than one occurrence will be counted if there is > 1 day gap between the end date of the preceding AE and the start date of the consecutive AE

For occurrence, the presence of at least one SAE / SAE suspected to be related to study treatment / non SAE has to be checked in a block e.g., among AE's in a ≤ 1 day gap block, if at least one SAE is occurring, then one occurrence is calculated for that SAE.

The number of deaths resulting from SAEs suspected to be related to study treatment and SAEs irrespective of study treatment relationship will be provided by SoC and PT.

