10.5.3.2 Adverse events (AEs)

All AEs recorded during the study will be summarized. The incidence of treatment-emergent AEs (new or worsening from baseline) will be summarized by primary system organ class, severity based on the National Cancer Institute's Common Terminology Criteria for Adverse Events (CTCAE) current edition version 4.03, type of AE, and relationship to the study drug by study Part. Deaths reportable as SAEs and non-fatal SAEs will be listed by patient and tabulated by primary system organ class, type of AE, and study Part.

Qualifying AEs will be separately listed by primary system organ class, worst grade based on the CTCAE current edition version 4 and type of AE. The DDS will be used.

Any other information collected (e.g. start/end dates and duration of AE, severity or relatedness to study medication) will be listed as appropriate. For patients undergoing intra-patient escalation to doses other than their initially received dose level, data up to the first intra-patient escalation will be summarized and all post-escalation data will only be listed.

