2.1 Data analysis general information

The data will be analyzed by Novartis personnel and/or designated CRO(s) using SAS version 9.4, and for Bayesian modeling, R version 2.13.2 and Winbugs 1.4.3. PK parameters will be calculated using non-compartmental methods available in Phoenix WinNonlin version 6.4 or above.

The data will be summarized with respect to demographic and baseline characteristics, efficacy observations and measurements, safety observations and measurements, and all relevant PK using descriptive statistics (n, mean, standard deviation, median, minimum, and maximum) for quantitative data and contingency tables (frequencies and percentages) for qualitative data.

Demographic and safety data will be summarized and listed by study treatment groups.

Study treatment groups refer to

- INC280 300 mg BID Capsule
- INC280 600 mg BID Capsule
- INC280 400 mg BID Tablet

Analyses of efficacy data may be summarized by study parts and revised definition of c-MET positivity, as introduced in Protocol Amendment 2; i.e. MET gene copy number ≥ 5 by FISH with c-MET IHC intensity score 2+ in $\geq 50\%$ of tumor cells or unknown, or c-MET IHC intensity score 3+ in $\geq 50\%$ of tumor cell, or presence of c-MET mutation:

- Dose Determining
- Dose Expansion
 - c-MET high
 - c-MET low

The cMET IHC and FISH analyses were performed through Novartis designated central laboratories.

All data collected for patients in the Dose-Determining part will be reported at the initial Dose-Determining dose level, irrespective of whether a patient undergoes intra-patient escalation to a higher dose level.

The statistical analyses will take into account the study treatment formulation as appropriate.

The primary and secondary endpoints (refer to [Section 1.2](#)) will be performed based on FAS. For more information please refer to [Section 2.7.1](#).

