1. ***pre-treatment period:*** from day of patient’s first informed consent to the day before first administration of study treatment
2. ***on-treatment period:*** from date of first administration of study treatment to 30 days after date of last actual administration of any study treatment (including start and stop date)
3. ***post-treatment period:*** starting at day 30+1 after last administration of study treatment.

Safety summaries include only data from the on-treatment period with the exception of baseline data which will also be summarized where appropriate (e.g. change from baseline summaries). In particular, summary tables for adverse events (AEs) will summarize only on-treatment events, with a start date during the on-treatment period (**treatment-emergent** AEs).

However, all safety AE data (including those from the pre-treatment period) will be listed.

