2.9.1.4 Adverse events of special interests

An adverse event of special interest (AESI) is a grouping of AEs that are of scientific and medical concern specific to Capmatinib. These grouping are defined using MedDRA terms, SMQs (standardized MedDRA queries), HGLTs (high level group terms), HLT (high level terms) and PTs (preferred terms). Customized SMQs (Novartis MedDRA queries, NMQ) may also be used. A NMQ is a customized group of search terms which defines a medical concept for which there is no official SMQ available or the available SMQ does not completely fit the need. It may include a combination of single terms and/or an existing SMQ, narrow or broad. For each specified AESI, the number and percentage of subjects with at least one event of AESI occurring during on-treatment period will be summarized:

- Overview of adverse events of special interest for Capmatinib

A listing of all grouping levels down to the MedDRA preferred terms used to define each AESI will be generated.

Note: From the eCSR, only risk where “Core Safety Risk” = Y should be selected to report Adverse events of special interest in the CSR (the available name in GPS, for “Core Safety Risk”, is SP).

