2.9.1.5 Death

On-treatment deaths will be produced by study treatment group, SOC and PT. All deaths will be listed using safety set, post treatment deaths will be flagged.

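### The SAP's AE and AESI summaries omit the protocol's cut at intra-patient escalation, so any AE starting after a Dose-Determining patient's switch would be counted under 300 mg bid (minor)

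*SAP*

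**What the plan says.** **The switch.** Protocol 4.1 allows a Dose-Determining patient, started on 300 mg bid capsules, to move to the Expansion dose after consultation with the sponsor, provided that the patient has had no dose reduction. Protocol Table 6-4 gives the Expansion starting dose as 600 mg bid for capsules and 400 mg bid for tablets.

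**The protocol's rule for AEs.** Protocol 10.5.3.2 opens with a general statement that every AE recorded in the study is summarised. Its last paragraph makes an exception for patients who escalate beyond their initial dose: "data up to the first intra-patient escalation will be summarized and all post-escalation data will only be listed".

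**The column.** Protocol Section 10 and SAP 2.1 carry the same sentence. Data of Dose-Determining patients are "reported at the initial Dose-Determining dose level, irrespective of whether a patient undergoes intra-patient escalation to a higher dose level".

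**The SAP's window and scope.** SAP 2.1.1 runs the on-treatment period from first dose "to 30 days after date of last actual administration of any study treatment", with no break at escalation. SAP 2.9.1.3 then says "AE summaries will include all AEs occurring during on-treatment period" and produces the tables by study treatment group. It adds: "A patient with multiple CTCAE grades for the same preferred term will be summarized under the maximum CTCAE grade recorded for the event". SAP 2.9.1.4 has the same scope for AEs of special interest: the number of subjects with "at least one event of AESI occurring during on-treatment period will be summarized".

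**Outputs with a separate purpose.** For trial registries, SAP 2.9.1.3 plans "two required tables on on-treatment adverse events which are not serious adverse events with an incidence greater than 5" per cent, and on serious events. SAP 2.9.1.5 says "On-treatment deaths will be produced by study treatment group, SOC and PT".

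**The concern.** The protocol has two rules that work together. One says which column a switched patient belongs to. The other says when that patient stops contributing to the AE summaries. The SAP keeps the first, leaves out the second, and states a scope that contradicts it. Read as written, the SAP puts an AE that starts at 600 mg bid into the 300 mg bid column.

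Safety and tolerability are a secondary objective, and the by-dose tables are where a reader would compare 300 mg bid with the higher dose. Events moved from the higher exposure to the lower one blur that comparison. SAP Section 1 also says the plan may serve as a reference for investigator's brochure updates, abstracts and manuscripts, so the tables could be used outside the study report.

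**Working it through.** The plan states no figure to reproduce. The check is a comparison of rules, followed by simple arithmetic for scale.

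**1. Follow one switched patient through both documents.** Take a patient whose first event of some preferred term starts after the move from 300 mg bid to the Expansion dose.

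- Column: 300 mg bid in both documents (Protocol Section 10, SAP 2.1).
- Within the summary window? Protocol 10.5.3.2: no, listed only. SAP 2.1.1 with 2.9.1.3: yes, because the event falls between first dose and 30 days after last dose.
- Result: not counted under the protocol; counted under 300 mg bid under the SAP.

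**2. Check whether the protocol contradicts itself.** The opening sentence of 10.5.3.2 is general. The escalation sentence in the same section is specific to patients who escalate. On an ordinary reading the specific sentence limits the general one. The Section 10 sentence fixes the column only and does not set the window. The protocol is therefore consistent, and the SAP departs from it.

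**3. Effect on a table row.** Protocol 1.2.1.2.2 gives 8 Dose-Determining patients. If k patients have their first event of a term after the switch, the SAP rule raises that term's 300 mg bid rate by k/8 and the protocol rule raises it by 0.

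- k = 0: 0/8 = 0 points
- k = 1: 1/8 = 12.5 points
- k = 2: 2/8 = 25 points

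The documents do not give the number of patients who switched, so k is an assumption. Its arithmetical range is 0 to 8. The conditions in Protocol 4.1 make the top of that range unlikely: a patient must have had no dose reduction, must have the sponsor's agreement, and must still be on treatment when the Expansion dose is confirmed.

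**4. Effect of the maximum-grade rule.** Suppose a patient has grade 1 of a term at 300 mg bid and a separate grade 3 event of the same term after the switch. The all-grades count does not change. Under the SAP the patient moves from the grade 1 cell to the grade 3 cell, so the grade 3 rate at 300 mg bid rises by 1/8 = 12.5 points. Under the protocol it stays at grade 1.

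**5. What is not touched.** The dose decision uses qualifying AEs from the first 28 days of treatment (Protocol 6.2.3, SAP 2.6), and the switch is available only once the Expansion dose has been confirmed (Protocol 4.1). TTP does not use AE data.

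**The case against.** Several points on the other side have force.

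- **The protocol itself says all AEs are summarised, and it attributes data by starting dose.** Both statements are there, and a table by starting dose is a legitimate convention. Neither removes the specific escalation sentence, which the SAP does not carry. It would still go too far to call the resulting columns false. They would show AEs by starting dose, and events would be added to the 300 mg bid column rather than hidden.
- **Possibly nobody switched.** This stands. A reader might infer that post-switch events are already mixed into the 300 mg bid results. The documents do not support that. Protocol 1.2.1.2.2 describes the 8 patients only as treated at 300 mg bid, and the study update under Amendment 2 mentions no switch.
- **The omission might be read as an undeclared change.** SAP Section 4 names only the dropped per-protocol-set analyses, so this inference is tempting. However, its lead-in covers protocol analyses that will not be performed because data are insufficient. It does not present itself as a full list of changes, and its silence does not show that the cut was abandoned. The table shells and programming specifications, which SAP Section 1 mentions, were not available and may contain it. If they do, SAP 2.9.1.3 as written would still conflict with them.
- **Exposure, dose intensity and laboratory tables also run through a switch.** A reader might extend the point to them. The escalation sentence sits in the protocol's AE section, and Protocol 10.3.1 and 10.5.3.4 set no such cut. Those summaries do not depart from the protocol.
- **Patient-level listings remain.** SAP 2.5.2 lists all doses and SAP 2.9.1.3 lists all AEs, so any misplaced event could be traced. This limits the harm without correcting the summary tables.

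**Conclusion.** The point holds as a minor one. A stated SAP rule for AE and AESI summaries conflicts with a specific protocol rule for patients who escalate. The size is conditional: 12.5 percentage points per affected patient and table row, assuming a denominator of 8, and zero if no patient switched. The effect is confined to descriptive tables for at most 8 patients. It does not reach the Expansion dose decision or the primary endpoint. The conclusion rests on reading the escalation sentence in Protocol 10.5.3.2 as limiting the general sentence that opens the section, and on the SAP text alone, without the table shells.

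**What to change.** Add one rule to SAP 2.9.1.3 and 2.9.1.4. In the by-treatment-group AE and AESI summaries, a Dose-Determining patient who switched contributes only AEs that start before the first dose above 300 mg bid. Later AEs are listed with a post-escalation flag. This wording covers a move to 600 mg bid capsules or to 400 mg bid tablets.

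Because the cut uses the AE start date, it deals with worsening only where the worse grade has its own record and start date. The SAP should say how a grade change within a single record is handled.

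Keep the registry tables and the death outputs complete, with a footnote identifying post-escalation events. Read literally, Protocol 10.5.3.2 would have such events listed only, so the SAP should state this as a deliberate exception.

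If no patient switched, say so in the SAP and leave the tables as they are. No change to the exposure, dose-intensity or laboratory summaries is needed.

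The cost is one rule with one exception, footnotes in the affected shells, and one switch date per switched patient from the Dosage Administration eCRF. No new data are required. If nobody switched, the cost is one sentence.
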